9.2. Non-Achondroplasia-Related Conditions of Medical Significance

The non-achondroplasia-related conditions of medical significance will be listed.

9.3. Physical Examinations

The number and percent of subjects with normal, abnormal, and clinical significant results will be calculated for each body system by visit and gender.

9.4. Collection of Blood Sample and X-ray of knees

The number and percent of subjects with blood sample collection, X-Ray of knees, and tibiofemoral angles measured will be described by visit and gender. Descriptive summaries of the tibiofemoral angles will be calculated and presented in a table.

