3. SUMMARY

PRODUCT NAME/NUMBER	Not applicable; no investigational treatment will be administered
PROTOCOL NUMBER	C4181001
DEVELOPMENT PHASE	N/A
PROTOCOL TITLE	An International, Prospective Registry Investigating the Natural History of Children with Achondroplasia
INDICATION	Achondroplasia
OBJECTIVES	To investigate the natural history of children with achondroplasia in terms of: 
 • Anthropometric characteristics; • Achondroplasia-related symptoms, tests, and treatments; • Biomarkers of bone growth.
STUDY DESIGN	This is a registry study in children with achondroplasia, age 0-15 years, to be conducted at multiple clinical sites globally. Children’s information will be collected in the registry at baseline and at every 3-month interval visits, for a maximum of 5 years. There will be a visit at Screening, Baseline, 3-month intervals, yearly (± 3 weeks) and an end of study Visit. The end of this study is defined as the date of the last visit of the last child participating in the study.
PLANNED NUMBER OF PARTICIPANTS	The total number of participants planned to be enrolled across all sites is approximately 300.
STUDY ENTRY CRITERIA	Inclusion criteria: The following criteria must be met for study inclusion: 
 1. Written informed consent/assent is obtained from the participant and/or parent(s)/legal guardian(s) before any study-related activity is carried out. 2. The participant/parent(s)/legal guardian(s) is able to provide written informed assent, where this is required according to national legislation, before any study-related activity is carried out. 3. The participant has been diagnosed as having achondroplasia documented by clinical diagnosis. 4. The participant is between 0 years and 15 years of age, up to day before 15th birthday, on the date of consent/assent. 5. The investigator has considered the family and prospective participating child being able to comply with the study procedures. Evidence of a personally signed and dated informed consent/assent document indicating that the participant (or a legally acceptable representative) has been informed of all pertinent aspects of the study. Participants who are willing and able to comply with scheduled visits, laboratory tests and other study procedures.

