8.1.3. Variables

Variable	Role	Data source(s)	Operational definition
Anthropometric Measurements	Analysis of growth parameters	Anthropometric measurements	Collection every 3 months & End of Study
Tanner Staging	Assess stage of sexual development	Physical Examination	Collection every 3 months & End of Study
Achondroplasia related complications, tests & treatments	Characterize treatments for Achondroplasia	Medical Records	Collection every 3 months & End of Study
Non-Achondroplasia	Characterize medical	Medical records	Collection every 3 months

Variable	Role	Data source(s)	Operational definition
co-morbidities and treatments	history		& End of Study
Biomarker Blood Sample	Analysis for potential biomarkers of bone growth	Blood sample	Blood sample every 12 months & End of Study
Activity Tracker & Gait Measurement	Analysis of daily activity & gait when walking	Activity Tracker & Gait Mat	Collection every 3 months & End of Study
Quality of Life	Assess Quality of Life in Participant & families with Achondroplasia	Questionnaire	Collection every 3 months & End of Study

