9.8.1. Sleep Disordered Breathing

- Has the participant ever been diagnosed with sleep-disordered breathing?
- Results of sleep tests/polysomnography including:
 - Date of test.
 - Conclusion/diagnosis of test.
 - Apnoea-hypopnoea index.
 - Was the test conducted on/off oxygen?
 - Was the test conducted on CPAP?
 - Is the test post-adenotonsillectomy (date of surgery if performed)?

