9.8.3. Orthopaedic Complications

- Imaging of the bones or knees.
- Tibial bowing including the dates of any surgery for.
 - Osteotomy.
 - 8-plates.
- Kyphoscoliosis including the presence of wedging on imaging and need for surgery.
- Lumbar lordosis.
 - Diagnosis of lordosis.
 - Presence of neurological signs in legs.
 - Impaired walking.

- Any surgical intervention.

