11. DATA ANALYSIS/STATISTICAL METHODS

11.1. Study Size

The sample size was not formally calculated. CCI

All analyses will be conducted on all enrolled participants.

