11.5. Data Analysis

Detailed methodology for summary and statistical analyses of data collected in this study will be documented in a statistical analysis plan (SAP), which will be dated, filed and maintained by the sponsor. The SAP may modify the plans outlined in the protocol; any major modifications of primary endpoint definitions or their analyses would be reflected in a protocol amendment.

As the main purpose of this study is to collect data to be used as reference for future interventional clinical studies, no hypothesis testing will be made.

A detailed master statistical analysis plan (SAP) will be developed covering the analytical principles and statistical techniques to be employed both for interim and final analysis. This study plans a primary master SAP, as well as supplemental SAPs. An advantage of this study design is its ability to answer questions that emerge during the study.

Subsequent and supplemental SAPs - triggered by new research questions emerging after the initial master SAP is developed or needed because the registry may evolve - can be developed when enough data become available to analyze a particular research question not included in the master SAP.

The main purpose of this study is descriptive.

Generally, descriptive statistics will be reported for all measured variables captured in this study. Derived Anthropometric measurements include:

- Annual Growth Velocity (AGV);
- Height Standard Deviation Score (SDS) with reference to normal population;
- Height SDS with reference to achondroplasia population;
- Sitting height/standing height (%) (or length: crown-rump length);
- Difference or ratio of Arm span/standing height/length (%);
- Knee height: lower segment length (lower segment=standing height – sitting height);
- Ratios between the cranial measurements taken.

Continuous (quantitative) variable summaries will include the number of participants (n) with non-missing values, number of missing values, mean and 95% confidence interval, standard deviation, median, minimum, and maximum.

Continuous variables may be classed into groups and analyzed as a categorical variable when appropriate. Categorical (qualitative) variable summaries will include the frequency and percentage of participants who are in the particular category or each possible value.

Event data will generally be listed. In case of frequent events tabulations might be considered.

Interim analyses will be performed on a regular basis.

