9.1. Related Symptoms, Tests, and Treatments

The number and percent of subjects reporting symptoms related to achondroplasia will be tabulated by gender, body system, and severity. The number and percent of subjects for each test and treatment related to achondroplasia will be described by gender.

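### Sleep studies, MRI and knee X-rays are unscheduled, but the SAP plans no complication rates among tested children and no age split for the tibiofemoral angle

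*SAP*

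**What the plan says.** **Scheduling.** Protocol Section 5 and SAP Table 2 both have a row for gathering information on achondroplasia-related tests, but neither schedules a sleep study, MRI or knee X-ray. Protocol 10.4 marks imaging assessments as not applicable. Protocol Section 15 lists the venous biomarker sample as the only qualifying procedure outside standard of care, and the risks in Section 6 mention no imaging.

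**Collection.** Protocol 8.1.3 gives medical records as the source for complications, tests and treatments; 9.9 lets parents or participants supply information too. The items include "Has the participant ever been diagnosed with sleep-disordered breathing" (9.8.1), "Imaging of the bones or knees" and wedging seen on imaging (9.8.3), and MRI results under cervical compression (9.8.4).

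**Analysis.** SAP 9.1 states "The number and percent of subjects reporting symptoms related to achondroplasia will be tabulated by gender, body system, and severity", then adds a count and percent for each test, by gender. SAP 9.4 counts children with a knee X-ray and with an angle measured, by visit and gender, and then states "Descriptive summaries of the tibiofemoral angles will be calculated and presented in a table". SAP 4.1 generally bases percentages on subjects with non-missing data, and SAP 6.1.2 imputes nothing.

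**Tables.** SAP Table 5 puts symptoms (14.3.6.1.1) and tests (14.3.6.1.2) in separate tables. The knee X-ray table (14.3.6.6) has no age-group label, although the pubertal status tables in the same list do. Protocol 11.5 asks for subgroups by gender, age group and their combination.

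**The concern.** Complication data are part of the primary objective, and achondroplasia-related adverse events are among the primary endpoints (Protocol Section 7). The registry is meant to serve as a reference for later interventional studies (Protocol 11.5). A complication that only a test can reveal is recorded only in children who had the test, so its percentage of enrolled children mixes disease frequency with testing frequency.

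If a later trial tested every child and compared its rates with this registry's percentages of enrolled children, part of any difference could come from testing alone. SAP 6.1.4 leaves site out of the analyses, with about 35 sites planned, so differences in local test ordering would not show in the tables.

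The tibiofemoral angle raises a separate problem. Its summary can cover only imaged children, and as written it may pool ages 0 to 15. If imaging depends on the state of the knees, or the angle varies with age, the pooled mean reflects who was imaged and at what age.

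**Working it through.** There is no plan figure to reproduce. The protocol says "The sample size was not formally calculated" and "no hypothesis testing will be made", and neither document gives a testing rate, a prevalence or an angle distribution. The check is therefore a reading of the denominators followed by an illustration with assumed rates.

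**Step 1: does the non-missing rule remove untested children?** Not reliably. The sleep item asks about a diagnosis ever made, so no is a valid, non-missing answer for a child never studied. Unless the eCRF codes such a child as unknown, the child stays in the denominator as unaffected.

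**Step 2: does a planned table link result to testing?** No. Symptoms and tests are tabulated separately, so percent positive among tested children appears nowhere.

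**Step 3: size for a complication that only a test reveals.** N = 300, from the protocol summary ("The total number of participants planned to be enrolled across all sites is approximately 300"). Assumed: true prevalence p = 30%, a perfectly accurate test, and every untested child recorded as no. Let t1 and t0 be the shares of affected and unaffected children tested.

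- Positives = N × p × t1
- Number tested = N × [p × t1 + (1 − p) × t0]
- Range = positives / N (untested all negative) to (positives + untested) / N (untested all positive)

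| t1 / t0 | Tested | Positive | % of enrolled | % of tested | Untested all positive |
|---|---|---|---|---|---|
| 50% / 50% | 150 | 45 | 45/300 = 15% | 45/150 = 30% | (45+150)/300 = 65% |
| 80% / 40% | 156 | 72 | 72/300 = 24% | 72/156 = 46% | (72+144)/300 = 72% |
| 90% / 20% | 123 | 81 | 81/300 = 27% | 81/123 = 66% | (81+177)/300 = 86% |
| 100% / 100% | 300 | 90 | 90/300 = 30% | 90/300 = 30% | 30% |

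With incomplete testing, the enrolled figure is below the true 30% in every row. The tested figure is right when testing is unrelated to disease and too high when affected children are tested more often. At p = 50% with 80% / 40% tested, the two figures are 120/300 = 40% and 120/180 = 67%.

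**Step 4: are the two percentages bounds?** No. With half tested and half of those positive, they are 75/300 = 25% and 75/150 = 50%, but the range the data allow is 25% to (75+150)/300 = 75%.

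**Step 5: tibiofemoral angle.** Let b be the share of children with bowing, and i1 and i0 the shares of bowed and unbowed children imaged. The bowed share among imaged children is s = b × i1 / [b × i1 + (1 − b) × i0]. With an assumed 10-degree difference between the groups, the mean shifts by 10 × (s − b).

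- i1 = i0 = 30%: s = b, shift 0.
- i1 = 60%, i0 = 20%: for b = 20%, s = 0.12/0.28 = 0.429, shift 2.3 degrees; for b = 40%, s = 0.24/0.36 = 0.667, shift 2.7.
- i1 = 80%, i0 = 10%: for b = 20%, s = 0.16/0.24 = 0.667, shift 4.7; for b = 40%, s = 0.32/0.38 = 0.842, shift 4.4.

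**The case against.** A reader might infer that the SAP treats every enrolled child as assessed. It does not. SAP 9.4 counts children X-rayed and measured, SAP 9.1 counts each test, continuous summaries show non-missing and missing numbers, and nothing is imputed. That part of the objection stands in full: the number imaged is already planned.

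A reader might also infer that children are imaged because bowing is suspected, so that the mean angle must overstate deformity. No passage gives the reason for imaging, and the shift is zero if imaging is unrelated to bowing.

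Three further points carry weight.

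- SAP 9.1 tabulates symptoms by body system and severity and names no row for sleep-disordered breathing, cervical compression or wedging. The shells are in a separate document. Whether and how these complications appear is therefore open.
- Every child has respiratory, neurological and musculoskeletal examinations at baseline and every three months (Protocol 9.3), so many complications can be found without a test. The point is confined to those that need one.
- Describing diagnosed burden under usual care is a legitimate aim of a descriptive registry, and the tibiofemoral angle is not an endpoint in Protocol Section 7 or SAP Section 2.2.

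The gap that remains is narrower: no table relates results to testing, the angle has no age split, and the visible limitations text in Protocol Section 13 does not mention selective testing.

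**Conclusion.** The concern holds as a risk to interpretation, not as demonstrated bias. For test-dependent complications, percentages of enrolled children may understate frequency, because an untested child can be recorded as no. How far depends on eCRF coding and testing patterns that the documents do not give. The illustrated sizes rest entirely on the assumed rates; they show that the effect can matter, not how large it is here.

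For the angle, the summary describes imaged children only. Neither the direction nor the size of any departure from the cohort can be read from the documents.

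The change is worth making because complications belong to the primary objective and it is cheap. The angle alone would be a lesser matter.

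**What to change.** 1. **SAP 9.1.** For sleep-disordered breathing, cervical compression on MRI and vertebral wedging, show number tested, percent positive among tested and percent among enrolled side by side. Label them as two denominators, not as bounds. If a range is wanted, count all untested children first as negative and then as positive.
2. **SAP 9.4 and Table 14.3.6.6.** Summarise the angle by age group, using the groups in SAP 6.1.5, at the visit or imaging date. Title it as imaged children only and state that it is not a population reference. Confirm that the eCRF holds the date: the protocol lists a test date for sleep studies (9.8.1), but none for knee imaging (9.8.3) or MRI (9.8.4).
3. **Limitations.** Add selective testing to Protocol Section 13 or the study report.
4. **Reconcile** the SAP's knee X-ray and tibiofemoral angle items with protocol 10.4. SAP Section 1 cites protocol version 2.0, whereas the protocol's document history runs to 3.0.

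The cost is SAP wording, a few table columns and less simple headline percentages, plus possibly one eCRF field if imaging dates are not held. No child needs a new test.

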9.5. Concomitant Medication

Concomitant medications will be summarized descriptively by anatomical therapeutical chemical (ATC) level 2 and PT and gender using counts and percentages.

Prior medications will be presented only in listings separately from concomitant medications. Medications that started prior to date of informed consent will be considered prior medications. Any medications continuing or starting post the date of informed consent will be considered concomitant. If a medication starts prior to the date of the informed consent and continues after the date of the informed consent, it will be considered both prior and concomitant.

Medications will be coded using ATC classification level 2 (WHO-DD v. March 2017).

10. Changes from Planned Analysis

No change have been planned.

11. Other Planned Analysis

Pubertal status for boys and girls will be described using number and percent of subjects reporting various categories by visit and age group at each visit. Only children ≥ 7 years of age will be included in the analysis, providing the investigator confirms there is no suspicion of a diagnosis of precocious puberty.

Descriptive summaries will be calculated for the biomarkers of bone growth. Longitudinal modeling of biomarkers of bone growth will done in a manner similar to modeling of anthropometric parameters. Additional analyses for the biomarkers of bone growth may be requested and described in a separate analysis plan.

12. References

1. Registries for Evaluating Patient Outcomes, 3rd edition. Informed Consent for Registries. In: Eds Gliklich RE, Dreyer NA, Leavy MB. Rockville (MD): Agency for Healthcare Research and Quality (US); 2014 Rockville (MD): Agency for Healthcare Research and Quality (US).
2. US Federal Register. (1998) International Conference on Harmonization; Guidance on Statistical Principles for Clinical Trials. Department of Health and Human Services: Food and Drug Administration [Docket No. 97D-0174]. Federal Register Volume 63, Number 179, pages 49583-49598. September 16, 1998.
3. ASA. (2016) Ethical Guidelines for Statistical Practice. Prepared by the Committee on Professional Ethics, April 2016. <http://www.amstat.org/about/ethicalguidelines.cfm>
4. RSS. (2014) The Royal Statistical Society: Code of Conduct, 2014. <http://www.rss.org.uk/Images/PDF/join-us/RSS-Code-of-Conduct-2014.pdf>.

13.1. Planned Table Descriptions

The following are planned summary tables for protocol number C4181001. The table numbers and page numbers are placeholders only and will be determined when the tables are produced.

Table 3: Demographic Data Summary Tables and Figures

Table/Figure Number	Population(s)	Table/Figure Title / Summary	Supporting Listing
14.1 Baseline and Demographic Data Summary Tables			
14.1.1	All Subjects	Subject Disposition	16.2.1.1 16.2.1.2
14.1.2	Screen Failures	Reason for Screen Failure	16.2.1.3
14.1.3.1	Enrolled Subjects	Summary of Demographics and Baseline Characteristics	16.2.4.1
14.1.3.2	Enrolled Subjects	Genetic Confirmation of Achondroplasia	16.2.4.4
14.1.3.3	Enrolled Subjects	Medical and Surgical History by System Organ Class and Preferred Term	16.2.4.2

Table 4: Anthropometric Data

Table Number	Population(s)	Table Title / Summary	Supporting Listing
14.2 Anthropometric Tables			
14.2.1.1	Enrolled Subjects	Standing Height in Children Aged ≥ 2 Years by Visit	16.2.6.1
14.2.1.2	Enrolled Subjects	Height in Supine Position in Children Aged < 2 Years by Visit	16.2.6.1
14.2.1.3	Enrolled Subjects	Sitting Height in Children Aged ≥ 2 Years by Visit	16.2.6.1
14.2.1.4	Enrolled Subjects	Crow-rump Length in Children Aged < 2 Years by Visit	16.2.6.1
14.2.1.5	Enrolled Subjects, Age groups	Knee Height by Visit	16.2.6.1
14.2.1.6	Enrolled Subjects, Age groups	Head Circumference by Visit	16.2.6.1
14.2.1.7	Enrolled Subjects, Age groups	Arm Span by Visit	16.2.6.1
14.2.1.8	Enrolled Subjects, Age groups	Elbow Extension Angle by Visit	16.2.6.1
14.2.1.9	Enrolled Subjects, Age groups	Knee Extension Angle by Visit	16.2.6.1
14.2.2	Enrolled Subjects, Age groups	Body Weight by Visit	16.2.6.2
14.2.3.1	Enrolled Subjects, Age groups	Cranial Series - Forehead Results by Visit	16.2.6.3
14.2.3.2	Enrolled Subjects, Age groups	Cranial Series - Top of Nose Results by Visit	16.2.6.3
14.2.3.3	Enrolled Subjects, Age groups	Cranial Series - Base of Nose Results by Visit	16.2.6.3
14.2.4.1	Enrolled Subjects, Age groups	Waist Circumference by Visit	16.2.6.4
14.2.4.2	Enrolled Subjects, Age groups	Chest Circumference by Visit	16.2.6.4
14.2.5.1.1	Enrolled Subjects, Age groups	Height Growth by Visit	16.2.6.5
14.2.5.1.2	Enrolled Subjects	Statistical Analysis of Height Growth: MMRM	16.2.6.5
14.2.5.2	Enrolled Subjects	Height Standard Deviation Score with Reference to Normal Population by Visit	16.2.6.6
14.2.5.3	Enrolled Subjects	Height Standard Deviation Score with Reference to Achondroplasia Population by Visit	16.2.6.6
14.2.5.4	Enrolled Subjects, Age groups	Ratio Between Sitting Height and Standing Height by Visit	16.2.6.7
14.2.5.5	Enrolled Subjects, Age groups	Ratio Between Arm Span and Standing Height by Visit	16.2.6.7
14.2.6.1.1	Enrolled Subjects, Age groups	Difference Between Arm Span and Standing Height Growth by Visit	16.2.6.5
14.2.6.1.2	Enrolled Subjects	Statistical Analysis of Height Growth: MMRM	16.2.6.5

Table 5: Safety Data

Table Number	Population(s)	Table Title / Summary	Supporting Listing
14.3 Safety Data			
14.3.6 Other Safety Data Summary Tables			
14.3.6.1.1	Enrolled Subjects	Achondroplasia-Related Symptoms by Body System and Severity	16.2.7.1
14.3.6.1.2	Enrolled Subjects	Achondroplasia-Related Tests	16.2.7.2
14.3.6.1.3	Enrolled Subjects	Achondroplasia-Related Treatments	16.2.7.3
14.3.6.2	Enrolled Subjects	Non-Achondroplasia-Related Conditions of Medical Significance	16.2.7.4
14.3.6.3	Enrolled Subjects	Abnormal and Clinically Significant Physical Examination Results	16.2.9.1
14.3.6.4.1	Enrolled Subjects, Age groups	Pubertal Status for Boys by Visit	16.2.9.2
14.3.6.4.2	Enrolled Subjects, Age groups	Pubertal Status for Girls by Visit	16.2.9.3
14.3.6.5	Enrolled Subjects	Concomitant Medications by ATC Level 2 and Preferred Term	16.2.9.4
14.3.6.6	Enrolled Subjects	Blood Sample Collection and X-Ray of Knees	16.2.9.5 16.2.9.6

13.2. Planned Listing Descriptions

The following are planned data and subject data listings for protocol number C4181001.

In general, 1 listing will be produced per CRF domain. All listings will be sorted by gender, site, and subject number. All calculated variables will be included in the listings.

In all listings a blank line will be placed between each subject. Within a data listing, if an item appears line after line (e.g., repetition of subject number), then only the first occurrence will be displayed.

In data listings, the information for a subject will be kept on 1 page if possible, rather than splitting a subject's information across pages.

Table 6: Planned Listings

Data Listing Number	Population	Data Listing Title / Summary
16.2 Subject Data Listings		
16.2.1 Subject Discontinuation/Completion		
Listing 16.2.1.1	All Subjects	Informed Consent and Assignment to Enrolled Population
Listing 16.2.1.2	Enrolled Subjects	Study Completion Status
Listing 16.2.1.3	Screen Failures	List of Reasons for Screening Failure
Listing 16.2.1.4	All Subjects	Visit Dates
